8.2 Central Imaging Independent Review

All on-study spiral CT/MRI scans for all patients enrolled in the study will be collected prospectively and submitted to a central imaging reader for archiving and storage and may be reviewed at the end of study at the request of Lilly. A central imaging reviewer blinded to treatment assignment will provide an independent review of tumor response and tumor progression for patients enrolled in the Phase 3. Film or electronic copies should be collected by the investigative sites and sent to the central image reader. Complete details regarding image handling and submission can be found in the Radiology Technical Manuals.

9.0 ADVERSE EVENTS

9.1 Definition of Adverse Events

9.1.1 Adverse Events

An AE is defined as any untoward medical occurrence in a patient or clinical investigation subject administered a pharmaceutical product that does not necessarily have a causal relationship with this treatment. An AE can therefore be any unfavorable and unintended sign (including an abnormal laboratory finding), symptom, or disease temporally associated with the use of a medicinal (investigational) product, whether or not related to the medicinal (investigational) product..

Investigators are responsible for:

- monitoring the safety of patients in this study and for alerting Lilly or its designee to any event that seems unusual, even if this event may be considered an unanticipated benefit to the patient,
- the appropriate medical care of patients during the study,
- documenting their review of each laboratory safety report, and
- following, through an appropriate healthcare option, AEs that are serious or otherwise medically important, considered related to study treatment or the study, or that caused the patient to discontinue study treatment before completing the study. The patient should be followed until the event resolves, stabilizes with appropriate diagnostic evaluation, or is reasonably explained. Frequency of follow-up evaluation is left to the discretion of the investigator.

Adverse event terms should be recorded concisely, using acceptable medical terms. When possible, a diagnosis (ie, disease or syndrome) rather than the component signs and symptoms should be recorded on the AE CRF (eg, congestive heart failure rather than dyspnea, rales, and cyanosis). However, signs and symptoms considered unrelated to syndromes or diseases are to be recorded as individual AEs on the CRF (eg, if congestive heart failure and severe headache are observed at the same time, each event is to be recorded as an individual AE). Only abnormal laboratory values that result in clinical sequelae or require medication for treatment should be recorded as an AE. The AE should not be recorded as a procedure or clinical measurement (ie, a laboratory or vital sign). The underlying reason for the procedure or the abnormal clinical measurements, and, whenever possible, a diagnosis, should be recorded. The diagnosis should be recorded; not the individual laboratory test name.

A pre-existing condition is one that is present at the start of the study and is reported as part of the patient's medical history. It should be reported as an AE if the frequency, intensity, or character of the condition worsens during study treatment.

"Death" as an outcome of an AE may occur and should not be reported as an AE, but the cause of death should be reported on the AE eCRF.

For the purpose of this study, progression of underlying malignancy is not considered an (S)AE. Hospitalization, prolonged hospitalization, or death due solely to the progression of underlying malignancy will be captured on the AE CRF, but may NOT be reported as an SAE. Clinical symptoms of progression may be reported as AEs if they cannot be determined to be exclusively due to the progression, or if they do not fit the expected pattern of progression for metastatic pancreatic cancer.

If there is any uncertainty about an AE being due to the progression of cancer, it should be reported as an (S)AE.

Lack of drug effect is not an AE in clinical studies because the purpose of the clinical study is to establish treatment effect.

Planned surgeries and nonsurgical interventions should not be reported as AEs unless the underlying medical condition has worsened during the course of the study.

9.1.2 Serious Adverse Events

An SAE is any AE from this study that results in 1 of the following outcomes:

- death
- initial or prolonged inpatient hospitalization
- a life-threatening experience (ie, immediate risk of dying)
- persistent or significant disability/incapacity
- congenital anomaly/birth defect
- important medical events that may not be immediately life-threatening or result in death or require hospitalization may be considered serious when, based upon appropriate medical judgment, they may jeopardize the patient and may require intervention to prevent 1 of the other outcomes listed in the definition above.

For the purposes of this trial, the following will NOT be considered SAEs:

- Hospitalizations <24 hours, or for planned surgeries or procedures.
- Progression of underlying malignancy as a stand-alone event term; clinical events associated with disease progression should be reported as AEs or SAEs as applicable.

Serious AEs, including death, caused by disease progression should not be reported unless the investigator deems them to be possibly related to study treatment.

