9.4 Reporting of Adverse Events

After the ICF is signed, study site personnel will record via eCRF the occurrence and nature of each patient's preexisting conditions, including clinically significant signs and symptoms of the disease under treatment in the study. In addition, study site personnel will record via eCRF any change in the preexisting conditions and any new conditions as AEs. Investigators should record their assessment of the potential relatedness of each AE to study treatment via eCRF.

At each visit assessment, all AEs either observed by the Investigator or one of the Investigator's professional collaborators, or reported by the patient spontaneously, or in response to a direct question will be recorded on the AEs eCRF, whether believed by the Investigator to be related or unrelated to the study medication. If any AE occurs after dosing with study medication, the patient should be followed with the appropriate treatment and close medical supervision. The AEs that started after signing the ICF and up to 30 days after the last dose of study drug(s) will be collected. The Investigator will record the AE on the CRF and will provide the date of onset, severity,

relationship to study medication, date of resolution (or the fact that it is still continuing), action taken, and outcome of the AE. A causality assessment will be made to determine whether or not the AE is thought to be drug related. Removal of a patient from the study because of AEs or changes in laboratory test values, whether by the Investigator or by the patient's own volition, should be reported to Lilly or designee promptly. Study site personnel must report any treatment discontinuations that result from AEs to Lilly or its designee via eCRF, clarifying, if possible, the circumstances leading to the discontinuation of treatment.

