9.4.1 Reporting of Serious Adverse Events

After signing the ICF, all AEs are recorded by the site in the eCRF. The SAE reporting to Lilly or designee begins after the patient has signed the ICF and has received study treatment. However, if an SAE occurs after signing the ICF, but prior to receiving study treatment, it needs to be reported ONLY if it is considered reasonably possibly related to the study procedure.

If an ongoing SAE that is considered related to study drug remains unresolved at the conclusion of the study treatment, additional follow-up must continue until resolution or stabilization of the SAE.

If an SAE is present at the EOT visit, the SAE (and associated AEs and concomitant medications) should be followed to resolution or until the Investigator assesses the subject as stable, or the subject is lost to follow-up or withdraws consent. Resolution/stable means the subject has returned to baseline state of health or the Investigator does not expect any further improvement or worsening of the event.

If study drug is discontinued because of an SAE, this information must be included in the SAE report.

Study site personnel must notify Lilly or its designee of any SAE within 24 hours of investigator awareness of the event via a Lilly-approved method. If alerts are issued via telephone, they are to be immediately followed with official notification on study-specific SAE forms. This 24-hour notification requirement refers to the initial SAE information and all follow-up SAE information.

Investigators are not obligated to actively seek AEs or SAEs in patients once they have discontinued and/or completed the study (the patient summary CRF has been completed). However, if the investigator learns of any SAE, including a death, at any time after a patient has been discharged from the study, and he/she considers the event reasonably possibly related to the study treatment or study participation, the investigator must promptly notify Lilly or the designee.

The Investigator has responsibility for notifying the relevant IRB of all SAEs or new safety information in accordance with international and local laws and regulations. It is the responsibility of Lilly or the designees to notify regulatory agencies of all SUSARS within the timeframes required by applicable local laws or regulations.

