12.1.1. Incidence of Adverse Events

The following TEAE/SAE listings and summaries will be produced:

- overview of TEAEs
- summary of TEAEs by PT (all grade and grade \geq 3)
- summary of TEAEs by SOC and PT (all grade and grade \geq 3)
- summary of TEAEs by PT and maximum grade (1-5)
- list of SAEs
- summary of SAEs by SOC and PT (all grade and grade \geq 3).

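### Protocol 9.1.2 contradicts itself on serious events caused by disease progression, so their entry into the all-cause SAE tables can depend on relatedness judged by an unblinded investigator

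*Protocol*

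**What the plan says.** Protocol 9.1.2 lists what does not count as an SAE. One bullet removes progression of the malignancy as a stand-alone term, then adds that "clinical events associated with disease progression should be reported as AEs or SAEs as applicable". It sets no condition on relatedness. The sentence that closes the section reads: "Serious AEs, including death, caused by disease progression should not be reported unless the investigator deems them to be possibly related to study treatment".

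Protocol 9.1.1 covers the same ground. Hospitalization or death due solely to progression "will be captured on the AE CRF, but may NOT be reported as an SAE". On symptoms it says: "Clinical symptoms of progression may be reported as AEs if they cannot be determined to be exclusively due to the progression". It also has a tie-breaker: "If there is any uncertainty about an AE being due to the progression of cancer, it should be reported as an (S)AE".

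Protocol 9.4 says that AEs seen or reported at a visit "will be recorded on the AEs eCRF, whether believed by the Investigator to be related or unrelated to the study medication". Protocol 9.4.1 opens with "After signing the ICF, all AEs are recorded by the site in the eCRF" and then describes SAE reporting to the sponsor as a separate step.

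On the analysis side, Protocol 7.6.2 tabulates treatment-emergent SAEs separately from drug-related ones. SAP 12.1.1 plans a "summary of SAEs by SOC and PT", and SAP 12.1.2 repeats the summaries for related events. The SAP has no rule for serious events caused by progression.

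**The concern.** An all-cause SAE table is meant to be free of causality judgments, which is why the plan tabulates related SAEs separately. If the closing sentence of 9.1.2 governs what is entered, a causality judgment comes first for one class of event: serious events that the investigator ascribes to progression.

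The trial is open-label (Protocol 2.2), relatedness is a matter of the investigator's clinical judgment (Protocol 9.3), and comparing safety between arms is a secondary objective (Protocol 2.1.2). About 150 sites would each have to choose among the rules.

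Equal exposure to the rule in the two arms cannot be taken for granted. Protocol 6.4 and 8.1.1 allow some Arm 1 patients to stay on treatment after initial progression, whereas patients on FOLFOX alone may not. Because the treatment-emergent window ends 30 days after treatment stops, the time around progression that falls inside it may differ by arm.

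**Working it through.** The plan has no figure to reproduce here. The check is a side-by-side reading, followed by a small calculation to show when a bias can arise.

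**Step 1. One event, four rules.** Take a patient hospitalized for a clinical event that the investigator ascribes to tumor growth.

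| Rule | Not thought drug-related | Thought possibly drug-related |
|---|---|---|
| 9.1.2, bullet | AE or SAE as applicable; here an SAE | SAE |
| 9.1.2, closing sentence | Not reported | Reported |
| 9.1.1 | AE CRF but not an SAE if progression is the sole cause; (S)AE if there is any doubt | Not solely progression, so (S)AE |
| 9.4 | Recorded as an AE | Recorded as an AE |

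The rules are compatible in the right-hand column and diverge in the left-hand one. Under the closing sentence, relatedness is what moves an event from one column to the other. The sharpest conflict lies inside 9.1.2. The closing sentence differs from 9.1.1 in its criterion (relatedness rather than sole cause), in its default (do not report, rather than report when in doubt) and, on a literal reading, in whether anything is captured.

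**Step 2. What the filter does to the table.** The documents give no rates, so everything here except the definitions is an assumption. Let b be the proportion of patients with an SAE unrelated to progression, q the proportion with a progression-caused serious event, and a the proportion of the latter called possibly related. Assume that b is equal in both arms and that the two kinds of event are independent.

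- True SAE rate: 1 − (1 − b)(1 − q)
- Reported SAE rate under the closing sentence: 1 − (1 − b)(1 − q·a)
- Spurious difference when q is equal in the two arms: (1 − b)·q·(a₁ − a₂)

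Take b = 0.30 and let q run from 0.10 to 0.40:

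| a₁ (Arm 1) v a₂ (Arm 2) | Spurious difference |
|---|---|
| 10% v 10% | 0 |
| 20% v 10% | 0.7 × 0.10 × 0.1 = 0.7 points, to 0.7 × 0.40 × 0.1 = 2.8 points |
| 30% v 10% | 1.4 to 5.6 points |
| 50% v 10% | 2.8 to 11.2 points |

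Swapping the arms reverses the sign.

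**Step 3. Level.** With q = 0.20 the true rate is 1 − 0.7 × 0.8 = 44%. The reported rate is 1 − 0.7 × 0.98 = 31.4% at a = 0.1 and 1 − 0.7 × 0.90 = 37.0% at a = 0.5. Under this rule the table understates SAEs in both arms whenever a is below 1.

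**Step 4. Equal attribution, unequal event rates.** With a = 0.1 in both arms, and q = 0.20 in one and 0.30 in the other, the true rates are 44% and 51%, a gap of 7 points. The reported rates are 31.4% and 32.1%, a gap of 0.7 points. Equal attribution therefore removes the spurious difference only if progression-event rates are also equal; otherwise it shrinks a real one.

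**The case against.** The strongest reply is that the closing sentence concerns reporting to the sponsor, not data capture. Protocol 9.4.1 separates the two, 9.1.1 puts hospitalization and death from progression on the AE CRF, and 9.4 records AEs regardless of relatedness. On that reading nothing goes unrecorded. This stands in part: AE capture is likely to survive. But 9.1.1 itself bars the SAE classification for events due solely to progression, and neither document says whether such entries keep a seriousness flag or how the SAE tables treat them. Their absence from those tables is therefore not ruled out.

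A second reply is that the tie-breaker in 9.1.1 applies in both arms and does not depend on relatedness. An event that may be drug-related is not solely due to progression, so much of the closing sentence can be squared with 9.1.1. That is fair, and it limits the problem. It does not reconcile the closing sentence with the bullet before it.

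A third reply points to backstops. OS counts death from any cause, SAP 12.1.4 summarizes all deaths in the ITT population by reason and period, SAP 12.8 summarizes hospitalizations by arm, and SAP 12.1.1 tabulates TEAEs of all grades and of grade 3 or higher. All of these stand. Nor do the documents show that the DMC sees only SAEs: Protocol 7.10 says that it reviews safety data.

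A reader might also infer that 9.1.1 and 9.1.2 state opposite rules. They do not: for events due solely to progression, 9.1.1 and the closing sentence of 9.1.2 both keep them out of SAE reporting.

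**Conclusion.** The inconsistency is real and should be corrected. Followed as written, 9.1.2 lets sites classify the same event differently, and its closing sentence can make SAE status depend on relatedness judged with knowledge of the arm. The effect is confined to serious events ascribed to progression; it does not reach the SAE comparison as a whole.

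If the closing sentence governs what enters the tables, SAE rates are understated in both arms. Bias in the between-arm difference is a risk, not something the text demonstrates. It might be inferred that a new agent in Arm 1 attracts attribution and so inflates SAEs there. The documents do not support that: Arm 2 also receives study drugs to which events can be attributed, and Protocol 1.2.5 itself associates both 5-FU and oxaliplatin with thrombocytopenia. It might also be inferred that the distortion amounts to a few percentage points. The figures above rest on assumed rates, run from 0 to 11.2 points and can change sign, so they show the mechanism and are not an estimate.

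**What to change.** Reconcile Protocol 9.1.1, 9.1.2 and 9.4 into one rule for both arms:

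- Remove the relatedness condition as far as data capture is concerned.
- Record on the eCRF, under its diagnosis and with a seriousness flag, any clinical event that meets a seriousness criterion, whatever its presumed cause.
- Exempt only the bare term for disease progression with no accompanying clinical event.
- State any exemption for disease-related events separately, as an exemption from expedited reporting to the sponsor and nothing more.

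In SAP 12.1.1, state that the all-cause SAE table includes these events regardless of relatedness, and add a supporting table that excludes those ascribed to progression. The supporting table requires that ascription to be recorded on the form.

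The cost is wording in three protocol sections and one SAP section, plus some additional SAE entries for disease-related events. Entries already made under the present wording can be checked against the hospitalization data collected for SAP 12.8.

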9.1.3 Unexpected Adverse Events

Unexpected AEs are defined as any AE, the nature, specificity, or severity of which is inconsistent with the Referenced Safety Information within the Guidance to Investigator section of the Clinical IB for AM0010 and the package inserts for the individual drugs that comprise FOLFOX.

9.1.4 Suspected Unexpected Serious Adverse Reaction (SUSAR) Definition

A suspected, unexpected, serious, adverse reaction (SUSAR) is any AE for which there is evidence to suggest a causal relationship between the study drug(s) and the AE and which is assessed as both unexpected and serious. An unexpected adverse reaction, ie, any untoward and unintended response to the study drug(s), is one for which the nature and severity is inconsistent with the applicable reference safety information (eg, IB or package insert of the approved drugs in the combination). Lilly has procedures that will be followed for the recording and expedited reporting of SUSARs that are consistent with global regulations and associated detailed guidances.

9.2 Grading of Adverse Events

If the NCI CTCAE v4.03 cannot be applied, the AE severity should be graded on the following scale:

- 1 = Mild: Usually transient; requires no special treatment and does not interfere with the patient's daily activities
- 2 = Moderate: Produces a low level of inconvenience to the patient and may interfere with daily activities. These events are usually ameliorated by simple therapeutic measures
- 3 = Severe: Interrupts daily activity and requires systemic drug therapy or other medical treatment.

- 4 = Life-Threatening: Places the patient, in the view of the Investigator, at immediate risk of death from the reaction as it occurred, ie, it does not include a reaction that, had it occurred in a more severe form, might have caused death.
- 5 = Death: Refers to **death related to an AE**. The AE resulted in the patient's death.

9.3 Relationship to AM0010 and/or FOLFOX

The investigator will interpret and document whether or not an AE has a reasonable possibility of being related to study treatment or a study procedure, taking into account the disease, concomitant treatments, or pathologies. A “reasonable possibility” means that there is a cause-and-effect relationship between the study treatment and/or study procedure and the AE. The Investigator or qualified Sub-Investigator is responsible for assessing the relationship to AM0010 and FOLFOX using clinical judgment and the following considerations:

- **No:** Evidence exists that the AE has an etiology other than the study drug(s). For SAEs, an alternative causality must be provided (eg, pre-existing condition, underlying disease, intercurrent illness, or concomitant medication).
- **Yes:** There is reasonable possibility that the event may have been caused by the investigational medicinal product.

9.4 Reporting of Adverse Events

After the ICF is signed, study site personnel will record via eCRF the occurrence and nature of each patient's preexisting conditions, including clinically significant signs and symptoms of the disease under treatment in the study. In addition, study site personnel will record via eCRF any change in the preexisting conditions and any new conditions as AEs. Investigators should record their assessment of the potential relatedness of each AE to study treatment via eCRF.

At each visit assessment, all AEs either observed by the Investigator or one of the Investigator's professional collaborators, or reported by the patient spontaneously, or in response to a direct question will be recorded on the AEs eCRF, whether believed by the Investigator to be related or unrelated to the study medication. If any AE occurs after dosing with study medication, the patient should be followed with the appropriate treatment and close medical supervision. The AEs that started after signing the ICF and up to 30 days after the last dose of study drug(s) will be collected. The Investigator will record the AE on the CRF and will provide the date of onset, severity,

relationship to study medication, date of resolution (or the fact that it is still continuing), action taken, and outcome of the AE. A causality assessment will be made to determine whether or not the AE is thought to be drug related. Removal of a patient from the study because of AEs or changes in laboratory test values, whether by the Investigator or by the patient's own volition, should be reported to Lilly or designee promptly. Study site personnel must report any treatment discontinuations that result from AEs to Lilly or its designee via eCRF, clarifying, if possible, the circumstances leading to the discontinuation of treatment.

9.4.1 Reporting of Serious Adverse Events

After signing the ICF, all AEs are recorded by the site in the eCRF. The SAE reporting to Lilly or designee begins after the patient has signed the ICF and has received study treatment. However, if an SAE occurs after signing the ICF, but prior to receiving study treatment, it needs to be reported ONLY if it is considered reasonably possibly related to the study procedure.

If an ongoing SAE that is considered related to study drug remains unresolved at the conclusion of the study treatment, additional follow-up must continue until resolution or stabilization of the SAE.

If an SAE is present at the EOT visit, the SAE (and associated AEs and concomitant medications) should be followed to resolution or until the Investigator assesses the subject as stable, or the subject is lost to follow-up or withdraws consent. Resolution/stable means the subject has returned to baseline state of health or the Investigator does not expect any further improvement or worsening of the event.

If study drug is discontinued because of an SAE, this information must be included in the SAE report.

Study site personnel must notify Lilly or its designee of any SAE within 24 hours of investigator awareness of the event via a Lilly-approved method. If alerts are issued via telephone, they are to be immediately followed with official notification on study-specific SAE forms. This 24-hour notification requirement refers to the initial SAE information and all follow-up SAE information.

Investigators are not obligated to actively seek AEs or SAEs in patients once they have discontinued and/or completed the study (the patient summary CRF has been completed). However, if the investigator learns of any SAE, including a death, at any time after a patient has been discharged from the study, and he/she considers the event reasonably possibly related to the study treatment or study participation, the investigator must promptly notify Lilly or the designee.

The Investigator has responsibility for notifying the relevant IRB of all SAEs or new safety information in accordance with international and local laws and regulations. It is the responsibility of Lilly or the designees to notify regulatory agencies of all SUSARS within the timeframes required by applicable local laws or regulations.

